- Patients will be followed for survival and further anticancer therapy information post progression via phone contact (with the patient's guardian, if applicable) approximately every 12 weeks.
- ^f A complete physical examination should include an evaluation of head, eyes, ears, nose and throat, neck, heart, chest (including lungs), abdomen, extremities, skin, lymph nodes, cardiovascular status and neurological status. A limited physical examination should include neurological status, and additionally be directed at the evaluation of symptoms or specific safety issues. Changes from baseline abnormalities should be recorded at each subsequent physical examination. New or worsened abnormalities should be recorded as AEs if appropriate.
- ^g Vital signs (systolic and diastolic blood pressure; pulse rate; and oral, and temporal or tympanic temperature) will be taken before study treatment and approximately 15 minutes prior to each collection of PK blood samples, if applicable, during the treatment period.
- ^h Hematology includes hemoglobin, platelet count, white blood cell (WBC) count, neutrophil count, and lymphocyte count. Per the Temodar package insert, hematology also needs to be completed on Day 43, which is 21 days after the second dose.
- ⁱ Chemistry includes albumin, alkaline phosphatase, aspartate aminotransferase (AST), alanine aminotransferase (ALT), blood urea nitrogen (BUN), chloride, creatinine, glucose, lactic acid dehydrogenase (LDH), phosphate, potassium, sodium, total bilirubin, and total protein.
- ^j Testing will be performed by the local laboratory at Screening and will include HBV serology (HBsAg, HBsAb, and HBcAb) and viral load assessment (HBV DNA).
- ^k Urinalysis will be assessed using urine dipstick. Urine microscopy will be performed if any assessment on the urine dipstick is abnormal. Urinalysis includes glucose, protein, ketones, bilirubin, blood, red blood cells, and white blood cells.
- ^l For women of childbearing potential, a serum pregnancy test must be performed during screening ≤ 7 days prior to Day 1. For subsequent pregnancy testing while on study treatment and at end of treatment, urine pregnancy tests are acceptable. If a urine pregnancy test is positive, a confirmatory serum pregnancy test is required.
- ^m Tumors will be assessed at screening by MRI per RANO criteria within 14 days prior to Day 1 and then approximately 4 weeks after completion of RT as part of the EOT visit. Patients without PD at the EOT visit must then be followed with MRIs every 8 weeks (± 7 days) during the Follow-up Phase.
- ⁿ All patients will receive daily pamiparib concurrent with RT starting on Day 1 for a time period that will be defined following review of the safety data obtained in Arm A, as outlined in [Section 4](#). Patients will be required to fast for at least 1 hour before and 2 hours after each pamiparib administration. Water is allowed during the fasting period. A dose of pamiparib should be skipped if it is not taken within 2 hours of the scheduled time. An extra dose of pamiparib should not be taken to make up for a missed dose. If vomiting occurs during the course of treatment, no re-dosing of the patient is allowed before the next scheduled dose. On days with PK assessments, pamiparib should be administered in the clinic.
- ^o All patients will receive temozolomide (TMZ) at a dose level as outlined in [Section 4.2.1](#) on the same schedule as pamiparib. Instructions for TMZ administration are the same as for pamiparib. Antiemetic prophylaxis may be provided as described in [Section 7.1.2.3](#). On days with PK assessments, TMZ should be administered in the clinic.
- ^p Adverse events and laboratory safety measurements will be recorded at each study visit, graded per NCI-CTCAE Version 4.03 and assessed as outlined in [Section 10](#).

After informed consent has been signed but prior to study treatment, only SAEs should be reported. After initiation of study treatment, all AEs and SAEs, regardless of relationship to study treatment, will be reported until 30 days after last study treatment or initiation of new anticancer therapy, whichever occurs first. After this period, the investigator should report any SAEs that are believed to be related to prior study treatment.

- ^q Concomitant medications will be recorded at each study visit. All concomitant medications taken by or administered to the patient within 28 days before Day 1 and 30 days after the last day of study treatment should be recorded. The eCRF entry must include the dose, regimen, route, indication, and start and stop dates of use of the prior and concomitant medications. Concomitant medications include subsequent anticancer therapy information acquired during the Follow-up Phase.
- ^r Pharmacokinetic samples will be collected from patients in all cohorts at the following time points: predose (within 30 min prior to dose) and 2 hours (\pm 30 min) post-dose on both Day 1 and Day 15. If pamiparib treatment is administered only for a 2-week (14-day) time period, PK samples will be collected on Day 1 and Day 14 instead. The time of study drug administration on the day prior to Day 15 (Day 14 for patients receiving only 2 weeks of pamiparib) must be recorded on the eCRF. Details concerning collection, processing, and handling of the PK plasma samples will be provided in the laboratory manual.
- ^s Blood samples must be collected at screening or on Day 1 (5 mL) for the assessment of germline mutations. Additionally, 3 blood samples (10 mL each) must be collected for the assessment of circulating tumor cells (CTCs) and plasma markers (eg, circulating nucleic acids [CNAs]) of GBM, TMZ treatment, and PARP inhibition at screening or on Day 1 before study treatment, and 2 blood samples (10 mL each) must be collected for the assessment of blood markers (eg CNAs) on Day 15 and Day 36 before study treatment and at the EOT visit (unless one had been collected within 14 days). Instructions for the processing, storage, and shipping of samples will be provided in the laboratory manual.

t

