4.1.1. Dose Escalation Phase (Phase 1b)

The Phase 1b, dose escalation phase consists of the following:

Arm A: Pamiparib (60 mg BID) administered continuously at increasing exposures of 2, 4, and 6 weeks in combination with RT administered for 6 to 7 weeks.

Arm B: Depending on the safety of the Arm A combination, the following combination may be explored: pamiparib (at the exposure determined as safe in Arm A) in combination with RT administered for 6 to 7 weeks and increasing doses of TMZ ([Section 4.2.1](#)).

In both Arms A and B, after RT is completed, patients will receive no further RT.

Maintenance Treatment for Arms A and B

Following completion of RT, at the discretion of the investigator and after discussion with the medical monitor, patients in the Arm A escalation and expansion and patients in Arm B escalation phases of the study may continue to receive pamiparib in combination with TMZ. TMZ will be given at a dose level lower than or equal to a dose that has been determined to be safe and tolerable in Arm C of study.

In the Arm B expansion phase of the study, maintenance treatment with pamiparib in combination with TMZ will be mandatory for all patients.

Dosing for this maintenance treatment should begin after the 4-week rest period (+ 7 days) to allow for recovery from RT treatment (please refer to [Appendix 1 Table 4](#)).

Arm C: Pamiparib (60 mg BID, administered continuously) in combination with increasing doses of TMZ ([Section 4.2.1](#)). TMZ will be administered on Days 1 to 21 of each 28-day cycle.

Approximately 60 patients may be enrolled in the 3 arms of the dose escalation phase. The actual sample size in this phase will depend on the number of dose escalation cohorts enrolled per arm.

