4.2. Details of Dose-Escalation Stage

4.2.1. Starting Dose and Dose-Escalation Approach

Arm A

RT will be administered QD × 5 days/week for 6 to 7 weeks with 1.8 or 2 Gy/fraction for a total target dose of between 58 Gy and 64 Gy.

The starting dose for pamiparib will be the 60 mg PO BID based on the rationale outlined in [Sections 1.3](#) and [1.4](#). In Cohort 1, exposure to pamiparib will be limited to the first 2 weeks of RT. In Cohorts 2 and 3, pamiparib will be given for the first 4 and 6 weeks of RT, respectively. If 2, 4, or 6 weeks of combination treatment exceeds the MTD, alternative regimens for pamiparib may be explored after discussions with all investigators based on which regimen exceeded the MTD and

what toxicities were observed. For example, if 2 weeks of pamiparib are not tolerated, a schedule of 1 week on, 1 week off, or 1 week on and 3 weeks off may be explored. Depending on data available at that time, a lower dose level of pamiparib may also be explored.

Arm B

The opening of Arm B will depend on the safety of the Arm A combination, and Arm B may be enrolled at the initial dose and schedule of pamiparib found to be safe and tolerable in Arm A. RT will be administered as for Arm A.

The first dose level of TMZ will be lower than or equal to a dose that has been determined to be safe and tolerable in Arm C, and dose escalation will proceed as described for Arm C. The time period of TMZ administration may be the same or shorter than that for pamiparib administration. Similar to Arms A and C, alternative regimens may be explored with adjustments of dose and/or schedule as outlined for Arms A and C.

Arm C

Since TMZ is given as a DNA-damaging sensitizer for pamiparib and to simplify TMZ dosing, flat-dosing will be used for TMZ. The first dose level of 40 mg QD corresponds to 23 mg/m^2 assuming an average body surface area of 1.73 m^2 . Subsequent dose levels of 80 mg and 120 mg correspond to 46 mg/m^2 and 69 mg/m^2 , respectively. Additional higher dose levels may be explored, and the TMZ dose will not be increased by more than 50% each time. TMZ will be given on Days 1 to 21 of each 28-day cycle based on data and rationale discussed in [Sections 1.2, 1.3, and 1.4](#).

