4.2.3. Assessment of Dose-Limiting Toxicity

Dose-limiting toxicities will be assessed during the DLT assessment window starting with the first day of study treatments for all cohorts. The following assessments must be obtained at the end of the DLT assessment window: complete physical examination, vital signs and weight, Eastern Cooperative Oncology Group (ECOG) performance status, ECG, hematology, chemistry, coagulation, urinalysis, AEs, and concomitant medications.

For Arm A, the DLT assessment window will depend on the time period of pamiparib administration during RT and will consist of the time period of combination treatment plus 4 weeks after the last scheduled combination treatment, eg, 6 weeks for Cohort 1 of Arm A when pamiparib is given during the first 2 weeks of RT, and 10 weeks for Cohort 3 of Arm A when pamiparib is given during 6 weeks of RT.

For Arm B, the DLT assessment window will depend on the time period of combined administration of pamiparib and TMZ during RT and will otherwise follow Arm A rules, eg, if TMZ will be given only for the first 3 weeks of pamiparib and RT, then the DLT assessment window will be 7 weeks.

For Arm C, the DLT assessment window will encompass the first cycle of 28 days.

Patients who withdraw or are withdrawn from the study prior to completing the DLT assessment window for reasons other than a DLT will not be considered evaluable for DLT and will be replaced if needed to meet patient number requirement for dose escalation. Patients who do not experience a DLT and who do not receive ≥ 42 Gy of RT (Arms A and B) and $\geq 70\%$ of scheduled pamiparib (Arms A, B and C) and TMZ (Arms B and C) dosing during the DLT assessment window will not be considered evaluable for DLTs and will be replaced if needed to meet patient number requirement for DLT assessment.

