6.3. Treatment

Day 1 of Cycle 1 is the first day of any study treatment administration (there is no Day 0 in this protocol).

Details on study treatment are provided in [Section 7.1](#).

Study procedures of each clinic visit are outlined in [Appendix 1](#).

On days with PK assessments, study drug should be administered in the clinic in accordance with the schedule for the PK samples. Assessments should be obtained before study drug administration unless stated otherwise in [Appendix 1](#) and should be performed in order of least invasive to most invasive assessment. All safety-related assessments must be reviewed and dose modifications, if necessary, be made by the investigator or subinvestigator before study drug administration.

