Appendix Table 1: Schedule of Assessments for Arm A (Pamiparib and Radiation Therapy) (Continued)

Study Phase	Screening ^a	Radiation Therapy (RT) ^b							Rest ^c		End of Treatment ^d	Safety Follow-up ^e	Long-Term Follow-up ^e
		RT D1	RT D8	RT D15	RT D22	RT D29	RT D36	RT D43	Rest D1	Rest D15			
Concomitant medication(s) ^p	X	X	X	X	X	X	X	X	X	X	X	X ^p	X (~q12w) ^p
Pharmacokinetics ^q		X		X									
Blood for biomarkers ^r	X	X		X							X		
Tumor tissue ^s	X												
Survival follow-up													X (~q12w)

-7/-14 to -1, Day -7/-14 to Day -1 of screening; aPTT, activated partial thromboplastin time; CSF, cerebrospinal fluid; D, day; ECG, electrocardiogram; ECOG, Eastern Cooperative Oncology Group; INR, International Normalized Ratio; MRI, magnetic resonance imaging; q8w ±7d, every 8 weeks ± 7 days; ~q12w, approximately every 12 weeks; RT, radiation therapy

- ^a Screening must occur within 28 days of Day 1. Some assessments have a narrower screening window as shown in the table. Assessments obtained within 14 days of Day 1 (pregnancy and laboratory assessments: within 7 days) do not have to be repeated on Day 1. It is highly recommended that general screening assessments such as physical examination and laboratory assessments should be conducted first to rule out ineligibility based on those grounds before more involved and/or invasive procedures are carried out.
- ^b RT will be administered once daily (QD) × 5 days/week for 6 to 7 weeks with 1.8 or 2 Gy/fraction for a total target dose of between 58 Gy and 64 Gy. If the time period of RT extends beyond 6 weeks, a clinic visit on Day 43 will be required (gray italics in table).
- ^c Day 1 of Rest Phase is defined as the day after RT is completed.

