- ^d For patients who have completed all study treatment per protocol and who do not continue on maintenance treatment with pamiparib in combination with TMZ, as described further below, the end-of-treatment (EOT) visit will occur at the end of the Rest Phase, 28 days after RT was completed. Patients who discontinued study treatment for any other reason outlined in [Section 6.5.1](#) will undergo the EOT visit within 7 days after stopping all study treatments. A visit should be scheduled as soon as possible, but the EOT visit may occur later after discussion with the medical monitor for specific circumstances, such as prolonged hospitalization. The visit at which MRI showed progressive disease (PD) may be used as the EOT visit provided that all required assessments were performed. MRI does not have to be repeated if it was performed within 14 days of the EOT visit or at a prior response evaluation that documented PD. ECG does not have to be repeated if it was performed within 14 days of the EOT visit.

After RT is completed, patients will receive no further RT. However, at the discretion of the investigator and after discussion with the medical monitor, patients may continue to receive pamiparib in combination with TMZ until PD, unacceptable toxicity or death, withdrawal of consent, loss to follow-up, or study termination by sponsor, as described in [Section 4.1.1](#) and [Section 4.1.2](#). This maintenance treatment should begin after the 4-week rest period post-completion of RT (+7 days) to allow for recovery from RT treatment. Patients should follow the Schedule of Assessments for the maintenance treatment ([Appendix 1 Table 4](#)).

- ^e Safety Follow-up: All patients who discontinue study treatment for reasons other than completion of RT per protocol will have a safety follow-up visit approximately

30 (± 7) days after the last day of study treatment to collect AEs and SAEs that may have occurred after the patient discontinued from the study treatment. For patients who have completed all study treatments per protocol, this safety follow-up coincides with the EOT visit.

Long-Term Follow-up: Patients who were not discontinued from study treatment due to PD and meet criteria otherwise (eg, discontinued for AE and no new anticancer therapy) will be followed every 8 weeks (± 7 days) until disease progression, administrative issues, start of other anticancer therapy or any other reason listed in [Section 6.7](#), whichever occurs first.

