- ⁿ All patients will receive daily pamiparib concurrent with RT starting on Day 1 for a time period that is determined by the Cohort a patient was enrolled into. Patients in Cohort 1 will receive daily pamiparib for the first 2 weeks of RT only (black X), patients in subsequent cohorts will receive pamiparib for longer time periods (gray italics X) as outlined in [Section 4](#). Patients will be required to fast for at least 1 hour before and 2 hours after each pamiparib administration. Water is allowed during the fasting period. A dose of pamiparib should be skipped if it is not taken within 2 hours of the scheduled time. An extra dose of pamiparib should not be taken to make up for a missed dose. If vomiting occurs during the course of treatment, no re-dosing of the patient is allowed before the next scheduled dose. On days with PK assessments, pamiparib should be administered in the clinic.
- ^o Adverse events and laboratory safety measurements will be recorded at each study visit, graded per NCI-CTCAE Version 4.03 and assessed as outlined in [Section 10](#). After informed consent has been signed but prior to study treatment, only SAEs should be reported. After initiation of study treatment, all AEs and SAEs, regardless of relationship to study treatment, will be reported until 30 days after last study treatment or initiation of new anticancer therapy, whichever occurs first. After this period, the investigator should report any SAEs that are believed to be related to prior study treatment.
- ^p Concomitant medications will be recorded at each study visit. All concomitant medications taken by or administered to the patient within 28 days before Day 1 and 30 days after the last day of study treatment should be recorded. The eCRF entry must include the dose, regimen, route, indication, and start and stop dates of use of the

prior and concomitant medications. Concomitant medications include subsequent anticancer therapy information acquired during the Follow-up Phase.

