- ^q Pharmacokinetic samples will be collected from patients in all cohorts at the following time points: predose (within 30 min prior to dose) and 2 hours (\pm 30 min) post-dose on both Day 1 and Day 15. Where pamiparib treatment is administered for only a 2-week (14-day) time period, the PK samples will be collected on Day 1 and Day 14 instead. The time of study drug administration on the day prior to Day 15 (Day 14 for patients receiving only 2 weeks of pamiparib) must be recorded on the eCRF. Details concerning collection, processing, and handling of the PK plasma samples will be provided in the laboratory manual.
- ^r Blood samples must be collected at screening or on Day 1 (5 mL) for the assessment of germline mutations. Additionally, 3 blood samples (10 mL each) must be collected for the assessment of circulating tumor cells (CTCs) and plasma markers (eg, circulating nucleic acids, CNAs) of GBM, TMZ treatment, and PARP inhibition at screening or on Day 1 before study treatment, and 2 blood samples (10 mL each) must be collected for the assessment of plasma markers (eg, CNAs) on Day 15 and Day 36 before study treatment and at the EOT visit (unless one had been collected within 14 days). Instructions for the processing, storage, and shipping of samples will be provided in the laboratory manual.

^s

Appendix Table 2: Schedule of Assessments for Arm B (Pamiparib, Radiation Therapy and Temozolomide)

Study Phase	Screening ^a	Radiation Therapy (RT) ^b							Rest ^c		End of Treatment ^d	Safety Follow-up ^e	Long-Term Follow-up ^e	
		RT D1	RT D8	RT D15	RT D22	RT D29	RT D36	RT D43	Rest D1	Rest D15				Rest D29
Day of Phase	-28 to -1													
Allowed time window			± 2	± 2	± 2	± 2	± 2	± 2	+ 3	± 3	+ 3			
Study Day	-28 to -1	1	8	15	22	29	36	43	43-50	57-64	71-78	Varies ^e	Varies ^e	
Informed consent	X													
Patient enrollment	X ^a													
Demographics and medical history	X													
Complete physical examination ^f	X				X				X		X			
Limited physical examination ^f		X	X	X		X	X	X		X				
Vital signs and weight ^g	X	X	X	X	X	X	X	X	X	X	X			
Height	X													
ECOG performance status	X	X			X				X		X			
12-lead ECG	X (-14 to -1)	X					X				X			
Hematology ^h	X (-14 to -1)	X	X	X	X	X	X	X	X	X	X	X		
Chemistry ⁱ	X (-14 to -1)	X	X	X	X	X	X	X	X		X	X		
Coagulation (INR and aPTT)	X (-14 to -1)										X			
Hepatitis B serology ^j	X (-14 to -1)													
Urinalysis ^k	X (-14 to -1)				X				X		X			
Pregnancy testing ^l	X (-7 to -1)				X				X		X	X		

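### SAP 6.5.6 tabulates ECGs at EOT only and omits the on-treatment ECGs in Appendix 1; for Arm A completers without maintenance, the EOT visit is 29 to 64 days after the last pamiparib dose

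*Protocol*

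**What the plan says.** **ECG schedule.** Appendix Tables 1 and 2 (Arms A and B) place 12-lead ECGs at screening, RT D1, RT D36 and EOT, whatever the length of pamiparib dosing. Appendix Table 3 (Arm C) places them at screening, Day 1 of every cycle and EOT. Appendix Table 4 (maintenance) has re-screening, Cycle 1 Day 1 and EOT. Protocol 4.2.3 adds an ECG at the end of the DLT window, which in Arm A lasts for "the time period of combination treatment plus 4 weeks after the last scheduled combination treatment". Protocol 8.4.3 allows further ECGs when clinically indicated.

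**Dosing in Arm A.** Section 4.1.1 describes the escalation as "Pamiparib (60 mg BID) administered continuously at increasing exposures of 2, 4, and 6 weeks". Footnote n of Appendix Table 1 says "Patients in Cohort 1 will receive daily pamiparib for the first 2 weeks of RT only", and Section 4.2.1 says "In Cohorts 2 and 3, pamiparib will be given for the first 4 and 6 weeks of RT, respectively".

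**The Day 1 ECG.** Section 6.3 says "Assessments should be obtained before study drug administration unless stated otherwise", so this ECG is pre-dose. Footnote a of Appendix Table 1 adds "Assessments obtained within 14 days of Day 1 (pregnancy and laboratory assessments: within 7 days) do not have to be repeated on Day 1". The screening ECG must itself fall within 14 days of Day 1 (8.4.3), so it can always stand in.

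**EOT in Arm A.** For completers who do not go on to maintenance, footnote d says "the end-of-treatment (EOT) visit will occur at the end of the Rest Phase, 28 days after RT was completed". An ECG from the previous 14 days can replace the EOT one.

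**Analysis.** Protocol 11.3.7 refers to ECGs performed as in Appendix 1 and reports the percentage with abnormal and clinically significant findings, with no visit limit. SAP 6.5.6 describes collection at screening and end of treatment, plus clinically indicated ECGs, and reports that percentage at EOT. SAP Section 8, which lists changes from the protocol's analysis, does not mention ECGs.

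**The concern.** The SAP's account of when ECGs are taken does not match the protocol's schedule, and its one ECG table is built on that account. In Arm A the visit it keeps is one at which most completers without maintenance have been off pamiparib for weeks. The visits it drops include those that fall on pamiparib: RT D36 on a 6-week schedule, and Cycle 2 Day 1 onward in Arm C.

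Safety of the combinations is a Phase 1b primary objective, and both documents say ECG findings will be used to determine safety. A reader of an EOT-only table could take a low rate of abnormal ECGs as evidence about pamiparib, when for these Arm A patients it describes ECGs with essentially no drug present. The table would also give no sign that the two shorter Arm A cohorts had no scheduled on-drug ECG during RT. In those cohorts no scheduled ECG could trigger the QTcF hold-and-discontinue rule in protocol Table 4 (Section 7.1.5.3) while the patient was taking pamiparib with RT.

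**Working it through.** Here on drug means on pamiparib, and last dose means the last pamiparib dose of the RT phase.

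**Reproducing the plan's own days.** RT of 6 or 7 weeks ends on Day 42 or 49. Rest D1 is the next day (43 or 50), and Rest D29, the EOT visit, is 42 + 29 = 71 or 49 + 29 = 78. Appendix Table 1 prints 71-78. The DLT window is weeks of combination plus 4: 2 + 4 = 6 weeks for Cohort 1 and 6 + 4 = 10 for Cohort 3, as 4.2.3 states.

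**Gap from last dose.** Gap = ECG day minus last dosing day. The RT D36 window is ±2 days (Days 34-38). The EOT window is +3 days (to Day 81). With the 14-day waiver, the earliest ECG that can serve for a Day 71 EOT visit is Day 57.

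| | 2 weeks (Cohort 1) | 4 weeks (Cohort 2) | 6 weeks (Cohort 3) |
|---|---|---|---|
| Last pamiparib day | 14 | 28 | 42 |
| RT D36 ECG | 20 to 24 days after | 6 to 10 days after | 4 to 8 days before (on drug) |
| End of DLT window (Day 42, 56, 70) | 28 after | 28 after | 28 after |
| EOT visit, Day 71-78 | 57-64 after | 43-50 after | 29-36 after |
| EOT at the +3-day limit | up to 67 | up to 53 | up to 39 |
| Earliest ECG usable as EOT | 43 after | 29 after | 15 after |

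**Drug remaining.** Fraction left = 2^(-t/half-life). Protocol 1.3.5.1 gives a half-life of about 13 h, range 5.4 to 34 h.
- Shortest EOT case, 15 days = 360 h: at 34 h, 360/34 = 10.6 half-lives, so under 0.1% remains.
- Shortest D36 case off drug, Cohort 2 on Day 34, 144 h: 0.05% at 13 h and 5% at 34 h.
- Cohort 1 on Day 34, 480 h: under 0.006% even at 34 h.

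**Required on-drug ECGs in the RT and rest phases, patients who complete the schedule.** Screening and RT D1 are before the first dose. The end-of-DLT-window and EOT ECGs are off drug in all three cohorts. Only RT D36 can count, so the totals are 0, 0 and 1 for Cohorts 1, 2 and 3.

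**What the EOT-only table leaves out.** It omits RT D36 (on drug on a 6-week schedule) and, in Arm C, Cycle 2 Day 1 and Day 1 of later cycles, when pamiparib is continuous. It also omits maintenance Cycle 1 Day 1, although under Section 6.3 that ECG precedes the first maintenance dose.

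**Patients.** SAP Section 5 gives 46 in Phase 1b, 40 in the Arm A expansion and 30 in the Arm C expansion: 46 + 40 + 30 = 116. The table covers all of them. The absence of any scheduled on-drug ECG during RT concerns about 6 to 12 patients, assuming 3 to 6 in each of Cohorts 1 and 2 under the rules in 4.2.2. Arm B or the Arm A expansion would be added only if a 2- or 4-week schedule was used there, which the documents do not state.

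**The case against.** The strongest reply is that little is lost. Protocol 10.1.5 requires ECG abnormalities judged clinically significant to be recorded as adverse events, and SAP 6.5.3 tabulates treatment-emergent events by arm and cohort and lists all events. A clinically significant on-drug tracing would therefore be reported. This stands. A reader might infer that on-drug ECG abnormalities would go unseen, and the documents do not support that. What is lost is the by-visit count, mainly of abnormal tracings not judged clinically significant.

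A reader might also infer that the missing on-drug ECGs in Cohorts 1 and 2 undermine the decision to extend dosing to 4 and then 6 weeks. That is not supported either. The dose is fixed at 60 mg BID, and Day 14 is already at steady state (336 h / 13 h = 25.8 half-lives; 336 / 34 = 9.9), so longer dosing does not raise concentration. Nonclinical QT findings are reassuring (1.3.4.1). The AU-002 summary (1.3.5.3) lists no cardiac or ECG event among its common related events, related Grade 3 events, DLTs or discontinuations, though it does not describe ECG monitoring. One ECG in each of 6 to 12 patients could not characterise QT in any case: zero events leaves a one-sided 95% upper bound of 1 - 0.05^(1/6) = 39% or 1 - 0.05^(1/12) = 22%.

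The day counts need two qualifications. They run from the last pamiparib dose; RT continues to about Day 42-49, so EOT is about 28 days after the last study treatment. They also apply only to completers without maintenance. Patients who stop all treatment early, Arm C patients and maintenance patients have EOT within 7 days of stopping, and a visit showing progression can serve as EOT, so their EOT ECG may be on or near drug.

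Finally, enrolment is complete, so changing the visit schedule cannot help these 116 patients. That is correct, and it confines the remedy for this study to the SAP.

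**Conclusion.** SAP 6.5.6 is wrong as written. It misdescribes the schedule in Appendix 1 and narrows the summary in Protocol 11.3.7 to one visit, without listing this as a change. For Arm A completers without maintenance, that visit is 29-36, 43-50 or 57-64 days after the last pamiparib dose on a 6-, 4- or 2-week schedule. The visit window can add up to 3 days, and the ECG itself can be up to 14 days earlier under the waiver. At every one of these gaps the ECG is off drug. The scheduled on-drug ECGs are left out of the table, and Cohorts 1 and 2 have none to report in the RT and rest phases.

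The size is minor: a reporting mismatch with an adverse event route that still catches what matters clinically. No primary efficacy endpoint or escalation decision is shown to be affected. The result rests on the scheduled days and on patients completing treatment as planned; the half-life range does not change it. The 6 to 12 patients rest on an assumed 3 to 6 per cohort.

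**What to change.** **For this study, in SAP 6.5.6:**
- Describe ECG collection as Appendix 1 schedules it.
- Tabulate abnormal and clinically significant ECGs by cohort and scheduled visit, including RT D36 and Arm C Cycle 2 Day 1 onward, with EOT as one of the visits.
- State that Arm A Cohorts 1 and 2 had no scheduled on-drug ECG in the RT and rest phases.
- List any remaining departure from Protocol 11.3.7 in SAP Section 8.

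The cost is a few sentences and one by-visit table from ECGs already scheduled.

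**For any future 2- or 4-week pamiparib schedule:** move the RT D36 ECG to the PK visit. That is Day 15 for 4 weeks; for 2 weeks, footnote q already says "the PK samples will be collected on Day 1 and Day 14 instead". Take the ECG after the in-clinic dose and before the 2-hour sample. Place it ahead of the vital signs that footnote g sets about 15 minutes before the sample, because 8.4.3 asks that blood draws and other procedures be avoided just before an ECG. State the post-dose timing in Section 6.3 and in the footnotes to Appendix Tables 1 and 2, and keep D36 for 6-week schedules.

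This adds no visit and no ECG. The off-drug D36 ECG is lost in the short-schedule cohorts, and their ECG would be post-dose while the 6-week cohort's stays pre-dose. On a 2-week schedule, Day 14 is the last dosing day, so the result could not change dosing during RT. This step does not apply to the 116 patients already enrolled.
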